3.2 Assessment of Subject Compliance

All infusions are given under the direct supervision of the clinical study team, so study agent compliance is insured.

3.3 Concomitant Medications and Procedures

All prescription medications, over-the-counter medications, non-prescription medications (including herbal medications), and concomitant surgical or interventional procedures will be recorded for up to 45 days after last MSC infusion. At the time of enrollment, study subjects may be currently receiving mesalamine, corticosteroids (≤ 20 mg daily, if body weight < 40 kg, up to 0.5 mg/kg/day), immunomodulators, or biologics. If the treating physician thinks that a medication dose should be lowered to avoid side effects, this should be recorded.

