In our study, toxicity will be scored as a binary variable indicating occurrence or non-occurrence over a monitoring interval from the start of MSC therapy to 45 days after the last infusion. Based on the planned administration schedule, the total toxicity monitoring period will have duration $28 + 45 = 73$ days. If we observe no severe (grade 3 or worse) adverse events in the young adult cohort, we will wait a minimum of 45 days before beginning to enroll 3 more patients, ages $12 \leq 16$ years (pediatric cohort). If we observe a severe (grade 3 or worse) adverse event occurring at any time from the start of therapy to 45 days following the last MSC administration in the young adult cohort we will stop the study. If we observe no SAEs attributed to MSC administration in the young adult cohort but an SAE (grade 3 or worse) occurring at any time from the start of therapy to 45 days following the last MSC administration in the pediatric cohort, we will stop the study. If patients with active disease do not have >grade 2 toxicity attributed to

cells and fail to rapidly progress with disease requiring urgent therapy or surgery, and at the discretion of the principal investigator, 4 additional weekly doses may be administered. Subjects are eligible to receive up to 4 additional doses of MSCs at weekly intervals, each of which will consist of the same cell number (1×10^6 cells/kg). The safety assessment period will be 45 days from the last dose administered. A maximum of 6 patients will be enrolled. Assuming an accrual rate of 3-4 patients per year, it is anticipated that it may require at least 18- 24 months to accrue all 6 patients. With the additional 24 months of follow up to evaluate longer-term safety and efficacy endpoints, the anticipated trial duration will be about 48 months.

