If we observe no severe (grade 3 or worse) adverse events in the young adult cohort, we will wait a minimum of 45 days before beginning to enroll 3 more patients, ages 12≤16 years (pediatric cohort). If we observe a severe (grade 3 or worse) adverse event occurring at any time from the start of therapy to 45 days following the last MSC administration in the young adult cohort we will stop the study. If we observe no severe adverse events attributable to MSC administration in the young adult cohort but a

severe (grade 3 or worse) adverse event occurring at any time from the start of therapy to 45 days following the last MSC administration in the pediatric cohort we will stop the study. A maximum of 6 patients will be enrolled. Assuming an accrual rate of 3-4 patients per year, it is anticipated that it will require at least 18 – 24 months to accrue all 6 patients. With the additional 24 months of follow up to evaluate efficacy endpoints noted in Section 2, the anticipated trial duration will be about 48 months.

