3.8 Treatment Phase (Day 0, 7, 14, 21)

On Days 0, 7, 14, and 21, subjects will arrive at the hospital for infusion of study drug, eligibility criteria, laboratory assessments, assessment of AEs/SAEs, collection of serum, saliva, urine and stool, and assessment of clinical indices.

Safety Monitoring Phase (Day 28, 45, 56, 73) +/- 3 days

During this visit, the patient will return to Children's National, or be seen by a local physician for a follow-up visit, physical exam, laboratory assessments, AEs/SAEs assessment, assessment of clinical indices, bloodwork, saliva, urine and stool collected for fecal calprotectin. Assessment of symptoms and screening for adverse events may be done by telephone if necessary.

Follow-up Phase (Day 180, 360, 720) +/- 28 days

Subjects will return to Children's National, or be seen by a local physician, for a physical examination and assessment of clinical indices. If physical examination is obtained by a local physician, reports will be emailed or faxed to the study investigator. Assessment of symptoms and screening for adverse events may be done by telephone if necessary.

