6 OFF TREATMENT AND OFF STUDY CRITERIA

Off Treatment Criteria for an Individual Subject

All patients, regardless of reason for withdrawal, will be asked to continue in the follow-up phase of the study. An individual subject may be withdrawn from the study for any of the following criteria:

- An individual subject's decision (the Investigator will attempt to determine the reason for the subject's decision).
- Non-compliance with the study medication and procedures to the extent that it is potentially harmful to the subject or to the integrity of the study data.
- Worsening of IBD symptoms as defined by a PCDAI greater than 50 or PUCAI greater than 65.
- Subjects requiring rescue treatment for IBD
- Any clinical AE, laboratory abnormality, or other medical condition or situation such that continued participation in the study would not be in the best interest of the subject (including changing medication doses due to concern for side effects).
- A change in the subject's baseline condition after enrollment, but prior to start of the treatment period so that the subject no longer meets the inclusion/exclusion criteria.
- The investigator deems a subject to be no longer fit to participate in the study.

Off Study Criteria for an Individual Subject

- Completion of study specified procedures.
- Refusal of further study follow-up by patient or legal guardian
- Lost to follow up
- Death
- Physician's discretion
- Patient withdrew from study
- Other

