7 STATISTICAL CONSIDERATIONS

7.1 Statistical Analysis Plan

7.1.1. Sample size and follow up. A maximum of 6 patients will be treated in this pilot study. It is anticipated that it will require 18-24 months to accrue 6 patients. With the additional 24 months of follow up to evaluate efficacy endpoints noted in Section 2, the anticipated trial duration will be 48 months.

7.1.4. Safety Monitoring and Stopping Rules. For the purpose of safety monitoring, "toxicity" will be defined as a probable or definite regimen related severe (grade 3 or worse) adverse event occurring at any time from the start of therapy to 45 days following the last MSC administration. If we observe 1 severe (grade 3 or worse) adverse event occurring at any time from the start of therapy to 45 days following the last MSC administration in the young adult cohort we will stop the study. If we observe no attributable severe adverse events in the young adult cohort, but do observe 1 severe (grade 3 or worse) adverse events occurring at any time from the start of therapy to 45 days following the last MSC administration in the pediatric cohort, we will stop the study.

7.1.3. Future Trials. If the trial is not stopped early, then the toxicity and efficacy data will be used to plan a future trial of MSC cell therapy in pediatric patients with either CD or UC, including (i) blinded placebo-controlled phase II trials optimizing dose or administration schedule, or (ii) randomized comparison to standard therapies.

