8 RECORDS TO BE KEPT

The CETI Research Office will maintain a password protected, restricted access database documenting the dates and doses of therapy as well as clinical chemistries and hematologic parameters. The clinical status and occurrence of any adverse events and subsequent interventions are to be kept on all patients.

- Imaging reports
- Surgical summaries
- Autopsy summaries, where appropriate

- Informed consent documents

All required clinical evaluation records will be the responsibility of Principal Investigator who will also be responsible for analysis of the clinical outcome and toxicity. The laboratory evaluation of immunological efficacy will be the responsibility of Principal Investigator.

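### Recording of medications and procedures ends at Day 73 (about Day 94 after eight doses), yet disease activity is scored for efficacy to Day 720

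*Protocol*

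**What the plan says.** Section 3.3 sets the end of recording. Prescription, over-the-counter and herbal medications, and "concomitant surgical or interventional procedures will be recorded for up to 45 days after last MSC infusion".

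Table 1 (Section 3.6) follows that rule. The Concomitant Medications row ends at Day 73, and so does the AEs/SAEs row. The disease activity row continues through Days 180, 360 and 720. The Follow-up Phase paragraph in Section 3.8 describes those three visits: the patient returns to the center "or be seen by a local physician, for a physical examination and assessment of clinical indices", with symptom and adverse event screening by telephone where needed. It does not mention medications or procedures.

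The protocol gives this long follow-up a purpose. Section 2.2 reads "With the additional 24 months of follow up to evaluate efficacy endpoints noted in Section 2", Section 7.1.1 repeats it, and Section 1.4.2 refers to "additional 24 months of follow up to evaluate longer-term safety and efficacy endpoints". Section 7.1.3 adds that the efficacy data will help plan the next trial.

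Two further provisions matter. Dosing can be extended: "Subjects are eligible to receive up to 4 additional doses of MSCs at weekly intervals" (Section 1.4.2). And Section 6, which lists the need for rescue treatment among its withdrawal criteria, states: "All patients, regardless of reason for withdrawal, will be asked to continue in the follow-up phase of the study".

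**The concern.** The patients have refractory disease, there is no control group, and the study treatment lasts four to eight weeks. Over two years some may start, switch or escalate a biologic, a steroid or an immunomodulator, or have surgery. A lower score at Day 360 after a new biologic would look the same as a lasting effect of the cells. The scores do not reveal it either: the only drug item in the CDAI as given in Appendix 3 concerns Lomotil or opiates for diarrhea.

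Because rescued patients are kept in follow-up, their late scores will be in the data. If the therapy that produced those scores is not recorded, an average late decline cannot be reliably separated from later treatment, and that average may be carried into the planning of the next trial. The SAP is not the place to solve this. It can define a strategy for scores after rescue, but it cannot apply one without knowing who was rescued and when.

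**Working it through.** This is calendar arithmetic and a count of table marks; no power formula applies.

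**Inputs**
- Infusions on Days 0, 7, 14 and 21 (Section 3.8; Table 1).
- Up to four more weekly doses (Section 1.4.2). With no break between the courses, which is an assumption, the eighth dose falls on Day 7 × 7 = 49.
- Recording ends 45 days after the last infusion (Section 3.3).
- Disease activity visits at Days 180, 360 and 720 (Table 1).

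**The protocol's own figure.** Section 2.2 gives the monitoring period as 28 + 45 = 73 days. This reproduces, and Day 73 is the last column with a medication mark.

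**Table 1 marks**
- Concomitant Medications: Screening and Days 0, 7, 14, 21, 28, 45, 56, 73 = 9.
- Disease activity: the same nine plus Days 180, 360 and 720 = 12.
- Scoring visits without a medication mark: 12 − 9 = 3, which are all the late visits.

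**Length of the gap.** There are two ways to count the end of recording: literally (last dose day + 45), or as the protocol counts its monitoring period (7 × number of doses + 45).

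| Doses | Counting | Recording ends | Days to Day 180 | Days to Day 720 | Share of 720 |
|---|---|---|---|---|---|
| 4 | Literal, 21 + 45 | Day 66 | 114 | 654 | 90.8% |
| 4 | Protocol's, 28 + 45 (last Table 1 mark) | Day 73 | 107 | 647 | 89.9% |
| 8 | Literal, 49 + 45 | Day 94 | 86 | 626 | 86.9% |
| 8 | Protocol's, 56 + 45 | Day 101 | 79 | 619 | 86.0% |

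The headline range of 626 to 647 days takes the last scheduled mark for four doses (Day 73) and the literal rule for eight (Day 94). The choice does not matter: every reading ends at least 79 days before Day 180.

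**Weight of one patient.** The protocol gives no rescue rate, so the likely shift in a late mean cannot be calculated. With at most 6 patients, one rescued patient contributes at least 1/6 = 16.7% of any late mean that includes that patient, and more if fewer patients are scored.

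**The case against.** The best reply is that later therapy will be found by other routes. Section 5.1 counts worsening of a baseline condition as an adverse event, so a flare that prompts new treatment qualifies. The Follow-up Phase paragraph allows for adverse event screening, and Section 8 says: "The clinical status and occurrence of any adverse events and subsequent interventions are to be kept on all patients". Section 8 also lists surgical summaries, and Section 8.1.4 expects the medical record to show other treatments. This stands in part: some rescue, particularly surgery, may be recoverable. It is not systematic, though. The adverse event row of Table 1 also stops at Day 73. Late visits may take place with a local physician, from whom only the examination report is required. The study database is built around the protocol-required assessments (Section 8.1.2), and late therapy is not one of them. A drug switched or escalated without a recorded flare need not appear at all.

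A second reply is that no late endpoint is fixed: the secondary endpoints name no time point, so the harm depends on an analysis the protocol does not specify. That is fair, and the concern applies only to late scores used for efficacy. But the protocol says three times that the long follow-up serves efficacy.

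Third, even a perfect medication log would not allow attribution in an uncontrolled study of six patients on permitted background therapy. That is true. The log would still separate patients who improved without new therapy from those who improved after it, which is the minimum a reader needs.

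Fourth, the share of days uncovered measures calendar time, not bias. This is also correct, and the percentages should be read that way. Finally, the 45-day limit matches the toxicity window and is sensible for the primary safety aim; it simply does not serve the efficacy follow-up.

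**Conclusion.** The concern holds. Section 3.3, Table 1 and the Follow-up Phase text agree that no recording of IBD therapy or procedures is scheduled at Days 180, 360 and 720, while the protocol scores disease activity at all three and assigns that period to efficacy. Between 86% and 91% of the 720 days are uncovered, whichever way the days are counted. The eight-dose figures assume uninterrupted weekly dosing.

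The consequence is limited. It touches secondary, descriptive results in at most 6 patients and leaves the primary safety endpoint alone. The size of any distortion is unknown because no rescue rate is given. It is still worth correcting, because the information is cheap to collect prospectively and may not be fully recoverable afterwards.

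**What to change.** - In Section 3.3 and Table 1, add one item at Days 180, 360 and 720: IBD therapy and IBD surgery since the previous visit, with drug or procedure, start date and reason. Request the same information when a local physician conducts the visit.
- Show each patient's rescue status wherever late scores are reported.
- While amending, name the assessment day in the treatment-failure rule of Section 3.4. As written, one cannot tell whether it was meant to cover the late scores. This is a drafting repair and the concern does not rest on it.

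The cost is one short case report form item at three visits that already exist. Late declines may look less favorable once rescued patients are identified.

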3.4 Prohibited Medications and Procedures

Concomitant non-steroid anti-inflammatory (NSAID) medications will not be permitted during study participation. Other medications used to treat IBD are prohibited other than those outlined in the eligibility criteria. Subjects required rescue IBD therapy before the day assessment will be considered treatment failures. Medications used to treat medical conditions other than IBD are permitted after review and approval of the Principal Investigator. Systemic immunosuppressant for conditions other than IBD is not permitted.

3.5 Study Schedule

Please see below table for detailed schedule of study procedures and assessments (table 1).

3.6 Table 1: Protocol of Events

Visits/Procedures	Screening visit	Treatment and Safety Monitoring phase									Follow-up Phase		
		Day 0 (Dose#1)	Day 7 (Dose #2)	Day 14 (Dose #3)	Day 21 (Dose #4)	Day 28	Day 45	Day 56	^a Day 73	Day 180	Day 360	Day 720	
Visit Day	Day -30 to -1												
Visit Window	Day -30 to -1	± 1 day ^b	± 3 days	± 3 days	± 3 days	± 3 days	± 3 days	± 3 days	± 3 days	±28 days	±28 days	±28 days	
Physical Examination	X					X	X	X	X	X	X	X	
Medical & Surgical History	X												
Informed Consent	X												
Active disease on sigmoidoscopy, colonoscopy, or MR enterography	X												
Vital Signs (temp, HR, RR, BP)	X	X	X	X	X	X	X	X	X				
SaO ₂ via pulse oximetry	X	X	X	X	X	X	X	X	X				
AEs/SAEs		X	X	X	X	X	X	X	X				
Concomitant Medications	X	X	X	X	X	X	X	X	X				
Eligibility Criteria		X											
Collection of serum ^c , saliva, urine, stool for research	X	X	X	X	X	X	X	X	X				
Urine pregnancy test (before each infusion)		X	X	X	X								
MSC infusion		X	X	X	X								
Disease activity assessed ^a	X	X	X	X	X	X	X	X	X	X	X	X	
Routine Labs													
CBC	X	X	X	X	X	X	X	X	X				
Electrolytes, liver enzymes, urinalysis	X	X	X	X	X	X	X	X	X				
Quantitative CRP, fecal calprotectin	X	X	X	X	X	X	X	X	X				

BMSCs

^aDisease activity assessed using: PCDAI, PUCAI, CDAI, Mayo, SES-CD

^bOnly applies to routine labs and pregnancy test

^cWe will draw up to 40 ml of blood at 9 time points for research studies (at baseline before the first infusion, before each subsequent infusion, and at the 45 day safety follow up).

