Study Design: This study is a pilot phase 1 study of patients with moderately to severely active Crohn Disease (CD) and ulcerative colitis (UC) (≥ 18 years, Mayo score: ≥ 6 or CDAI: > 220 ; < 18 years, Pediatric Crohn's Disease Activity Index (PCDAI) > 30) or Pediatric Ulcerative Colitis Activity Index (PUCAI) > 34). [1] [2] A fixed dose will be studied: 1×10^6 cells/kg administered intravenously (IV) weekly for 4 consecutive weeks, with the option of an additional 4 weeks of treatment, at the discretion of the principal investigator. The primary outcomes are regimen-related toxicity, defined in section 5. Toxicity will be scored as a binary variable indicating occurrence or non-occurrence over a monitoring interval from the start of MSC therapy to 45 days after the last infusion. Based on the planned administration schedule of 4 weeks, the total toxicity monitoring period will have duration $28 + 45 = 73$ days. If additional weekly doses are administered, the safety assessment phase will be 45 days after the last dose given.

Three young adult patients (ages 17≤22 years) will be enrolled, staggered by at least 7 days, and monitored for toxicity over a period of 73 days. Infusions are administered over the first 28 days, followed by a 45 day monitoring period. If we observe no severe (grade 3 or worse) adverse events in the young adult cohort, we will wait a minimum of 45 days after the last MSC administration before beginning to enroll 3 more patients, ages 12≤16 (pediatric cohort). If we observe a severe (grade 3 or worse) adverse event occurring at any time from the start of therapy to 45 days following the last MSC administration in the young adult cohort we will stop the study. If we observe no severe adverse events attributable to MSCs in the young adult cohort but a severe (grade 3 or worse) adverse event occurring at any time from the start of therapy to 45 days following the last MSC administration in the pediatric cohort we will stop the study. A maximum of 6 patients will be enrolled. Assuming an accrual rate of 3-4 patients per year, it is anticipated that it will require at least 18-24 months to accrue all 6 patients.

Eligibility

This protocol allows for the treatment of both male and female pediatric and young adult patients, between the ages of 12 ≤ 22 years, with active moderate to severe CD or UC, who have failed to respond to, or are intolerant of, biologic therapy.

Inclusion criteria

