3 STUDY AGENT

3.1 Preparation Administration, and Dosage

On the day of each infusion, the following procedures/assessments will be performed:

- MSCs will be thawed, harvested, counted, the viability will be determined, and appropriate samples will be sent for other release testing (including sterility). Vital signs (heart rate, blood pressure, respiratory rate, and temperature) will be measured within 15 minutes prior to the infusion (time 0) and then every 5 minutes during the infusion. If vital signs are normal after three 5-minute checks, they will be checked every 15 minutes during the remainder of the infusion, and then at 30 and 60 minutes after the infusion for 1 hour.
- Patients will be monitored according to institutional standards for administration of blood products and at a minimum will be monitored according to below:
 - Patients should remain in the clinic for at least one hour
 - Patients should remain on continuous pulse oximetry for at least 30 minutes

- Vital signs should be monitored at the end of the infusion then at 30 and 60 minutes
- Per institutional guidelines, pre-medication, consisting of oral acetaminophen (10-15 mg/kg/dose, max 650 mg) and diphenhydramine (0.5-1 mg/kg/dose, max 50 mg), will be administered at least 30 minutes prior to the infusion.
- No other medications should be given during the infusion, unless determined medically necessary by the treating physician.
- Supplemental oxygen will be kept by the bedside at all times.
- MSCs suspended in Plasmalyte A (multiple electrolyte injection) will be given as an IV infusion using weight-based dosing. We plan to infuse $1-4 \times 10^6$ cells per mL, not to exceed 240 mL. With a mean weight of 40 kg, the infusion volume would be 40-120 mL.
- Cells will be infused on Day 0 followed by repeat infusions weekly over a total of 4 weeks. An additional 4 weekly doses may be infused at discretion of physician. An attempt will be made to administer repeat infusions from the same initial donor, but administration of MSCs from another donor is permitted if same-donor cells are unavailable. Tracking of donor sample identification information will be performed for each sample.

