3.9.1 Phlebotomy

Research blood will be drawn during screening visit, treatment phase, and safety monitoring phase but will not exceed 2 cc/kg or a maximum of 40 ml per blood draw.[53] Blood tests run (CBC, CMP, CRP) are considered standard of care. However, additional tissue specimens (urine, saliva, blood, and stool) may be collected and banked, if the subject provides consent.

Any remaining specimens that will be stored for future research will be stored safely and securely in a research specimen storage laboratory at the CETI Laboratory at CNMC.

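### Optional extra doses carry the 45-day safety window past the last scheduled AE and laboratory visit, by 21 days after eight unbroken weekly doses

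*Protocol*

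**What the plan says.** The planned course is four weekly infusions on Days 0, 7, 14 and 21. Section 3.1 adds: "An additional 4 weekly doses may be infused at discretion of physician". Section 1.4.2 sets the conditions: no toxicity above grade 2 attributed to the cells, no rapid progression needing urgent treatment, and the principal investigator's agreement.

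The safety window follows the last dose. The synopsis says "If additional weekly doses are administered, the safety assessment phase will be 45 days after the last dose given", and section 1.4.2 says "The safety assessment period will be 45 days from the last dose administered". The stopping rule in section 7.1.4 counts a grade 3 or worse event "occurring at any time from the start of therapy to 45 days following the last MSC administration".

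The visit calendar does not follow the last dose. Section 3.8 lists the "Safety Monitoring Phase (Day 28, 45, 56, 73) +/- 3 days", and Table 1 shows the same days. Table 1 has no columns for doses 5 to 8. Its marks for AEs and SAEs, blood tests, vital signs and concomitant medications all stop at Day 73. The next visits are Days 180, 360 and 720 (± 28 days), with physical examination and disease activity only. For both the safety and the follow-up phases, section 3.8 adds "Assessment of symptoms and screening for adverse events may be done by telephone if necessary".

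Footnote c to Table 1 gives the research draws as "9 time points for research studies (at baseline before the first infusion, before each subsequent infusion, and at the 45 day safety follow up". Section 3.9.1 says "Research blood will be drawn during screening visit, treatment phase, and safety monitoring phase".

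**The concern.** The window is defined relative to the last infusion, and the visits that should observe it are fixed relative to Day 0. The two agree for four doses. Each extra dose moves the end of the window a week later while the last safety visit stays put.

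The window carries real decisions. A single grade 3 or worse event inside it stops the study. A clean window in the three young adults opens enrolment of patients aged 12 to 16, after a wait of at least 45 days from the last administration. If the last young adult had eight doses, that step could be taken without a scheduled AE or laboratory check at the end of the window. Toxicity seen only in the laboratory is the most exposed, because no blood count or liver enzymes are scheduled after Day 73. Section 3.3 also asks for concomitant medications to be recorded for 45 days after the last infusion, which the table's marks do not reach in these patients.

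**Working it through.** **Inputs.** Infusions on Days 0, 7, 14 and 21 (3.8, Table 1); up to four more at weekly intervals (1.4.2); window to 45 days after the last dose (synopsis, 1.4.2, 7.1.4); last safety visit Day 73 ± 3; next visit Day 180 ± 28. The protocol gives no start date for extra doses, so I assume no break after dose 4, which is the favourable case.

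**The plan's own figure.** 28 + 45 = 73 days, which reproduces and equals the last safety visit. Counted strictly from the fourth infusion on Day 21, the window closes at 21 + 45 = Day 66. Either way the Day 73 visit covers it.

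**Extra doses.** For k weekly doses, the last dose is on Day 7(k − 1) and the window closes on Day 7(k − 1) + 45. The uncovered time is that day minus 73, or minus 76 if the last visit is at its latest permitted date; negative results are set to 0.

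| Doses | Last dose | Window closes | Days past Day 73 | Days past Day 76 |
|---|---|---|---|---|
| 4 | Day 21 | Day 66 | 0 | 0 |
| 5 | Day 28 | Day 73 | 0 | 0 |
| 6 | Day 35 | Day 80 | 7 | 4 |
| 7 | Day 42 | Day 87 | 14 | 11 |
| 8 | Day 49 | Day 94 | 21 | 18 |

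For eight doses, 21/45 = 47% of the post-dose window lies after the last safety visit. The earliest next visit is 180 − 28 = Day 152, which is 152 − 94 = 58 days after the window has closed.

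**Sensitivity.** With a 7-day break before dose 5, the eight-dose gap is 49 + 7 + 45 − 73 = 28 days; with a 14-day break it is 35. Under the protocol's looser 28 + 45 counting, eight doses give 56 + 45 = Day 101, again a 28-day gap, and the gap then begins with the first extra dose (35 + 45 = Day 80, 7 days).

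**Footnote c.** The row marks screening and Days 0, 7, 14, 21, 28, 45, 56 and 73: 1 + 4 + 4 = 9, which agrees with the stated number and with 3.9.1. The footnote's list gives 1 + 3 + 1 = 5 draws for four doses and 1 + 7 + 1 = 9 for eight. So the number is right for the row, while the listed occasions are not those of the row.

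**The case against.** The strongest reply is that the text already extends the safety phase. Section 1.4.2 promises follow-up through the 45 days after the last infusion, 5.5 monitors AEs at every visit, and 10.1 provides continuous review. On this reading Table 1 simply prints the base course, and staff would move the visits. That is fair as to intent: a reader might infer that the plan means to stop monitoring at Day 73, and the documents do not support that. But none of these passages moves a visit. The days are fixed at ± 3, and monitoring at each visit does not help where no visit falls between Day 76 and Day 152.

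The second reply is that 18 to 21 days is not far outside the spacing already accepted: the base schedule has gaps of 45 − 28 = 17 and 73 − 56 = 17 days. A visit also looks back over the interval before it, and patients often report grade 3 events unprompted. This stands against calling nearly half the window unmonitored. What is missing is the closing check, above all the laboratory one.

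Third, extra doses are optional, barred after attributed toxicity above grade 2, and possible in at most six patients. The protocol does not say how many would receive them. This limits how often the gap arises and leaves its size unchanged.

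Two further inferences are tempting. One is that the nine draws in footnote c are a miscount; they match the row and 3.9.1, and the list itself reaches nine for an eight-dose course. The other is that the viral-specific T-cell endpoint loses its after-treatment sample. The row has blood before treatment and, for eight doses, at Days 56 and 73, which are +7 and +24 days after the last infusion. The endpoint asks only for before and after, so it is met.

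**Conclusion.** The schedule as written does not cover the safety window once two or more extra doses are given without a break. The shortfall is 7, 14 and 21 days for six, seven and eight doses (4, 11 and 18 if the last visit falls on Day 76), and longer with any break. With four or five doses the nominal schedule suffices. The figures rest on counting 45 days from the last infusion and on uninterrupted weekly dosing. Spontaneous reports, or telephone screening around Day 180, may still bring an event to light, but no scheduled AE check or laboratory test closes the window that governs stopping and the opening of the paediatric cohort. This should be corrected. The footnote mismatch is clerical, and no harm to an endpoint follows from it.

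**What to change.** In Table 1 and section 3.8, time the safety visits at +7, +24, +35 and +52 days after the last infusion. For four doses this gives 21 + 7, 21 + 24, 21 + 35 and 21 + 52, that is Days 28, 45, 56 and 73 as now. For eight unbroken doses it gives Days 56, 73, 84 and 101. Carry the AE/SAE, laboratory, vital-sign and concomitant-medication marks through to the +52 visit. That visit falls 52 − 45 = 7 days after the window closes, so it covers the window even at 3 days early. Add columns for doses 5 to 8 with the same pre-infusion checks as doses 2 to 4.

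Separately, reword the list in footnote c so that it names the visits marked in its row and agrees with 3.9.1.

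The cost is a wording change to the table and one section. Four-dose patients keep their dates. Patients given extra doses have later safety visits, to Day 101 for eight doses and beyond that if there is a break.
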